7.11 Pharmacogenomics

A whole blood sample for deoxyribonucleic acid (DNA) isolation will be collected before dosing on Day 1 from each participant in the study. The DNA samples will be analyzed to evaluate drug metabolic enzyme and transporter polymorphisms that may contribute to the variability in PK of PLN-74809. Detailed instructions for the handling and shipping of samples will be provided in the study manual.

7.12 Exploratory Efficacy Assessments

7.12.1 Spirometry

Absolute FVC volume and FVC percent of predicted will be assessed by spirometry at screening and at the timepoints specified in the Schedule of Events ([Appendix 1](#)). A historical value may be used if it has been completed within 1 month from the Baseline visit.

FEV1 will be assessed by spirometry at screening. A historical value may be used if it has been completed within 1 month from the Baseline visit.

7.12.2 *Patient-reported Outcome (PRO)*

Study participants will respond to a VAS for cough severity at the timepoints specified in the Schedule of Events ([Appendix 1](#)).

7.13 *Concomitant Medication and Adverse Event Assessments*

At each study visit, participants will be asked about how they are feeling and what medications they are taking (have started/stopped, adjusted dose, etc.).

7.14 *Missed Assessments*

Missed assessments will be reported as such and will not be imputed.

7.15 *Appropriateness of Measurements*

Collagen accumulation within the lungs of patients with fibrotic lung disease, particularly those with IPF, is the hallmark of disease progression and associated with substantial mortality. The changes in the PET ligand ^{68}Ga -CBP8 correlate with disease progression and may be a more sensitive measure of active disease, with ^{68}Ga -CBP8 preferentially binding to recently synthesized collagen over mature, organized collagen. Consistent with the mechanism of action of PLN-74809, changes in the PET ligand ^{68}Ga -CBP8 will support the role of ^{68}Ga -CBP8 as an important biomarker of disease activity, as well as evidence of PD effect and efficacy of PLN-74809 (decrease in collagen levels) in participants with IPF.

Collection of AEs, safety labs, vital signs, physical examinations and ECG recordings are standard well-established parameters to assess the safety and tolerability of pharmacological agents.

PK samples will be analyzed according to predefined validated analytical methods to assess the concentrations of PLN-74809 in plasma.

FVC is a standard measure collected according to current ATS guidelines for the measurement of IPF progression. The VAS scale for the assessment of cough will follow recommendations from the ERS Guidelines ([Morice et al, 2007](#)).

When available, appropriate standard guidelines will be used.

8 SAFETY ASSESSMENTS

8.1 Timing

In this study, AEs will be collected from the time the participant signs the ICF until the participant's last study visit.

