3 INVESTIGATIONAL PLAN

3.1 Overall Study Design and Plan

This is a Phase 2a, single-center, randomized, double-blinded, placebo-controlled study to evaluate type 1 collagen deposition in the lungs following once-daily (QD) treatment with 160 mg PLN-74809 for 12 weeks in participants with IPF.

The study consists of an up to 28-day screening period, a 12-week treatment period, and a 2-week (± 3 days) post treatment follow-up period.

Potential participants who provide written informed consent will be screened for study eligibility up to 28 days before administration of the first dose of study drug. Approximately 12 eligible participants will be randomized in a 2:1 ratio (160 mg PLN-74809 vs placebo; 8 receiving PLN-74809 and 4 receiving placebo) on Day 1 (Visit 3). Study treatment will be administered once daily for 12 weeks. Randomization will be stratified by use of standard of care (SoC) IPF therapy with pirfenidone or nintedanib (SoC use; yes or no).

^{68}Ga -CBP8 PET/MRI scans will be conducted within 7 days prior to baseline and at or within 7 days prior to Week 12, as indicated in the Schedule of Events ([Appendix 1](#)).

Participants who discontinue study drug for safety reasons prior to completion of 12 weeks of treatment will be encouraged to remain in the study to complete all remaining assessments; if this is not feasible, they will be asked to return to the clinic for an Early Termination (ET) visit for follow-up evaluations. If a participant elects to withdraw from the study after the 6th week of randomization, an end of participation ^{68}Ga -CBP8 PET/MRI will be offered to the participant to enhance appropriate data capture.

Potential acute exacerbations, respiratory-related hospitalizations, and/or respiratory-related deaths will be reviewed by an adjudication committee.

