6.2 Dose Modifications and Interruptions

There will be no dose modifications of the study drug. If the study drug needs to be interrupted for safety or tolerability issues, this should happen, as feasible, in consultation with the Sponsor Study Director, who together with the Investigator will assess and decide whether the study drug interruption should be temporary or permanent on a case by case basis. Participants who discontinue study drug for safety reasons prior to completion of 12 weeks of treatment will be asked to remain in the study to complete all remaining assessments; if this is not feasible, then they will be asked to return to the clinic for an early termination visit.

Dose modifications or interruptions of pirfenidone or nintedanib treatment may be implemented only for safety and tolerability reasons (e.g., liver enzyme elevation; see [Section 9](#)), in accordance with their corresponding prescribing information and in consultation with the Sponsor Study Director. This should not affect the administration of the study drug or the continuation of participants in the study.

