8.8.3 Reporting Serious Adverse Events

In order to meet the requirements for expedited reporting of SAEs meeting specific requirements to applicable regulatory authorities and Institutional Review Boards (IRBs)/ Independent Ethics Committee (IECs)/ Research Ethics Boards (REBs), all SAEs must be reported to the Sponsor per the Study Manual within 24 hours from the time site personnel first become aware of the event by completing the SAE form and emailing it to the below:

[contact]

Initial notification of an SAE by telephone must be confirmed in writing within 24 hours by completing the SAE form. As further information regarding the SAE becomes available, such follow up information should be documented and sent to ***[contact]***.

All SAEs must be followed by the Investigator to resolution or medical stabilization.

Withdrawal from the study in the event of a SAE and therapeutic measures taken shall be at the discretion of the Investigator. A full explanation for the discontinuation from the study should be made in the eCRF.

8.8.4 *Reporting SAEs to Regulatory Authorities and IRB/IEC/REB*

The reporting of any SAEs to applicable regulatory authorities will be the responsibility of the Sponsor in compliance with applicable country regulations. All SAEs must be reported to the IRB/IEC/REB by the Investigator in accordance with their regulations.

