- Obtain a history of concomitant drug use (including nonprescription or over-the-counter medications and herbal and dietary supplement preparations), alcohol use, recreational drug use, and special diets
- Rule out acute viral hepatitis types A, B, C, D, and E; alcoholic hepatitis; hypoxic/ischemic hepatopathy; and biliary tract disease
- Obtain immunoglobulin G1 (IgG-1), antinuclear antibody (ANA), anti-smooth muscle antibody (anti-SMA), anti-liver-kidney microsome type 1 (anti-LKM1), and anti-liver cytosolic antigen type 1 (anti-LC1) levels to be compared with baseline values, to rule out autoimmune hepatitis
- Obtain a history of exposure to environmental chemical agents
- Consider a gastroenterology or hepatology consultation, which may include a liver biopsy, for definite diagnosis

For participants with confirmed elevations in liver enzymes (as described above) warranting temporary interruption of study drug but not meeting permanent drug discontinuation criteria as stated above, more frequent hepatic laboratory testing and clinical assessments must be conducted using unscheduled visits, including a thorough causality evaluation and in consultation with the Sponsor Study Director.

Reinitiation of study drug can only be considered if another etiology is identified and confirmed and if liver abnormalities have returned to baseline values. **The decision to restart study drug must be discussed and approved in consultation with the Sponsor Study Director prior to reinitiation.**

Participants who permanently discontinue study drug due to potential liver toxicity must be followed for close monitoring until abnormalities stabilize to baseline levels or baseline grade of abnormality and the participant is asymptomatic. Participants should be encouraged to remain in the study and completed all scheduled visits and assessments. Long-term follow-up information should be provided for participants who permanently discontinue drug due to potential liver toxicity, including information on immunosuppressive therapy and new liver histology.

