Any participant who experiences a QTc prolongation not confirmed upon repeat ECG assessment may continue or resume administration of study drug and follow the scheduled study visits, if clinically appropriate. More frequent clinical evaluation and ECG monitoring through use of unscheduled visits is allowed, if clinically warranted.

Participants who permanently discontinue study drug due to potential QTc prolongation must be followed for close monitoring until abnormalities stabilize to baseline levels or baseline grade of abnormality and the participant is asymptomatic. Participants should be encouraged to remain in the study and completed all scheduled visits and assessments. Long-term follow-up information should be provided for participants who permanently discontinue drug due to confirmed QTc prolongation, including information on corrective therapy and cardiology consultation, if applicable.

11 **EARLY DISCONTINUATION OF STUDY OR INDIVIDUAL PARTICIPANTS**

In accordance with the Declaration of Helsinki, participants have the right to withdraw from the study at any time for any reason. The Investigator or Sponsor may withdraw a participant from the study or discontinue study drug for any of the following reasons:

- Noncompliance with protocol procedures including those relating to administration of study drug
- A serious or intolerable AE occurs
- Infection with COVID-19 that precludes safe participation in the study
- A clinically significant change in a laboratory parameter occurs
- Confirmed elevations in serum ALT or AST meeting criteria for suspected acute DILI (see [Section 9](#))
- Prolonged ECG QTc interval meeting criteria for permanent discontinuation (see [Section 10](#))
- Male participants whose female partners become pregnant during the study must stop the medication immediately
- The Sponsor or Investigator terminates the study
- The participant requests to be discontinued from the study

If a participant is withdrawn from the study or discontinues study drug, they will undergo early termination assessments; refer to the Schedule of Events ([Appendix 1](#)).

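### A participant who leaves outright can have 0 days of post-treatment adverse-event follow-up, because collection stops at a last visit with no set interval after the last dose (minor, inexpensive to improve)

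*Protocol*

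**What the plan says.** - **Collection.** Protocol 8.1: "AEs will be collected from the time the participant signs the ICF until the participant's last study visit". Section 12.6.1 repeats the rule.
- **TEAE definition.** Protocol 12.6.1 gives a start (first administration of study drug) and no end. The end comes from the SAP alone: both bullets in 5.12.1 close at completion of the last study visit.
- **Planned follow-up.** Protocol 3.1 provides for "a 2-week (± 3 days) post treatment follow-up period". Appendix 1 puts Visit 8 at Day 84 ± 3 days and Visit 9 at Day 98 ± 3 days.
- **People who stop early.** Under Protocol 6.2, those who stop drug for safety reasons "will be asked to remain in the study to complete all remaining assessments". If that is not feasible, Protocol 3.1 says "they will be asked to return to the clinic for an Early Termination (ET) visit for follow-up evaluations". Section 11 asks for early-termination assessments after withdrawal or drug discontinuation. None of these gives an interval from last dose to the ET visit. Footnote j of Appendix 1 foresees drug being taken in the clinic at the ET visit, where applicable.
- **How events are found.** Protocol 7.13: "At each study visit, participants will be asked about how they are feeling and what medications they are taking".

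**The concern.** For completers, ending collection at the last visit gives about two weeks of observation off drug. For an outright leaver the same rule can give none. A new event a few days after a same-day ET visit would not be actively sought. If it were reported anyway, it would meet the protocol's TEAE definition but fall outside the SAP's, so it would appear in the listings and not in the TEAE tables.

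Safety and tolerability is the trial's only secondary objective, and the sample size is justified by safety, tolerability and PK. With four placebo and eight active participants, one event more or less in a table is visible. What is at stake is equal ascertainment for a small group, mainly people still taking drug who leave for a non-safety reason. The primary analysis is not affected.

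**Working it through.** **Inputs.** 4 weeks screening, 12 weeks treatment and 2 weeks follow-up (Protocol 3.3); follow-up window ± 3 days (3.1); Visits 8 and 9 at Day 84 ± 3 and Day 98 ± 3 (Appendix 1); 8 active and 4 placebo (3.1). The documents give no drop-out rate.

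**1. Reproduce the plan's own figure.** 4 + 12 + 2 = 18 weeks, as Protocol 3.3 states. From first dose, 84 + 14 = 98 days, matching Visit 9.

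**2. Post-treatment observation for a completer.**
- Nominal: 98 − 84 = 14 days.
- From the stated ± 3 days: 14 − 3 = 11 to 14 + 3 = 17 days.
- Combining both visit windows (Visit 8 on Days 81 to 87, Visit 9 on Days 95 to 101): 95 − 87 = 8 to 101 − 81 = 20 days.

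**3. Post-treatment observation for an outright leaver.** With the ET visit on the day of the last dose: 0 days. The shortfall is 14 days nominally, 11 to 17 on the stated window, and 8 to 20 if both visit windows are combined.

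**4. Could the ET visit inherit the Day 98 date?** It shares the Visit 9 column in Appendix 1. But it exists for people who cannot complete the remaining assessments, so Day 98 cannot be their rule. SAP 5.2.7 summarizes ET data only when the visit coincides with a scheduled one, which presumes ET visits at other times.

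**5. Scale, for illustration only.** The SAP reports participant incidence and event counts, so no planned output uses these denominators.

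| Denominator | Person-days | 14 days as a share |
|---|---|---|
| All planned TEAE time, 12 × 98 | 1,176 | 1.2% |
| Active, 8 × 98 | 784 | 1.8% |
| Placebo, 4 × 98 | 392 | 3.6% |
| All post-treatment time, 12 × 14 | 168 | 8.3% |
| Active post-treatment time, 8 × 14 | 112 | 12.5% |
| Placebo post-treatment time, 4 × 14 | 56 | 25% |

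With an 11- or 17-day shortfall the first row becomes 11/1,176 = 0.9% or 17/1,176 = 1.4%. Assuming 0 to 2 such leavers, the nominal total is 0 to 28 person-days, or 0% to 28/1,176 = 2.4%.

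**6. What a 14-day rule recovers.** A leaver with last dose and ET visit on Day 42 is now observed for 42 days and would be observed for 42 + 14 = 56. That is 14 of the 98 − 42 = 56 missing days (25%). For Day 70 it is 14 of 98 − 70 = 28 (50%). The remaining shortfall is not recovered.

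**The case against.** The case against acting is substantial. Collecting to the last visit is a clear rule, consistently stated. Several provisions narrow the gap:

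- Safety discontinuers are asked to stay for all remaining assessments.
- Protocol 9: "Participants who permanently discontinue study drug due to potential liver toxicity must be followed for close monitoring until abnormalities stabilize". Protocol 10: "Participants who permanently discontinue study drug due to potential QTc prolongation must be followed for close monitoring until abnormalities stabilize".
- Protocol 8.8.3: "All SAEs must be followed by the Investigator to resolution or medical stabilization". That section also requires SAEs to be reported within 24 hours of site awareness, sets no end date itself, and refers to a Study Manual that is not available here.
- Spontaneous reports are recorded (8.8.2), unscheduled visits are possible, and SAP 5.12.1 lists every reported event.

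These points stand, and they limit the importance. They do not close the gap: they cover people who remain, problems already known, or events that someone volunteers. None actively seeks new events after the ET visit in an outright leaver.

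It also stands that a 0-day interval is a permitted extreme rather than the evident intent. The documents give no half-life value for the drug, so 14 days rests on parity with the planned follow-up and not on pharmacology. Leavers who withdraw consent to contact will yield nothing under any rule.

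A reader might infer that early discontinuers in general lose safety follow-up, that serious events after departure go unreported, or that the tables will favour the active arm. The documents support none of these. Safety discontinuers have a route to full follow-up, the SAE reporting section sets no cut-off, and nothing indicates which arm would lose participants or events. Nor would a late event in someone who already has a TEAE change overall TEAE incidence.

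**Conclusion.** The point holds as a minor improvement. An outright leaver can have 0 post-treatment days of adverse-event follow-up, against a planned 11 to 17 (8 to 20 if the two visit windows are combined), and the SAP's cut-off would keep a late-reported event out of the TEAE tables although the protocol's definition admits it. What is exposed is new-onset, mainly non-serious events in people who leave outright.

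The size depends on how many leave that way, which is unknown and may be zero, and on how soon after the last dose their ET visits fall. The person-day shares above indicate scale only. In a descriptive study of 12, whose listings can be read one participant at a time, this is neither an analysis error nor a material safety gap.

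**What to change.** For early terminators only; completers are unchanged.

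1. **Protocol 8.1 and 12.6.1.** Continue AE and SAE collection to the later of the last study visit or 14 days after the last dose. If no visit falls at or after day 14, including when no ET visit takes place, existing staff make one AE enquiry on days 14 to 17 after the last dose, using the open question in 7.13, provided the participant still consents to contact.
2. **SAP 5.12.1, both TEAE bullets.** Use a fixed cut-off: the later of the last study visit or last dose + 14 days. An onset on day 16 learned of at a day-17 call is then listed and not tabulated, without ambiguity. Flag in the listings anyone whose last contact came before the cut-off.
3. **SAP 5.2.10.** For events found at that enquiry, impute a missing stop date from the last contact. The current rule uses the last clinic visit and could place the stop before the start.
4. **Appendix 1, footnote j.** State whether drug is taken at the ET visit. If it is, count the 14 days from that dose.

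**Cost.** Items 1 and 4 are a protocol amendment, which Protocol 14.1 sends for IRB and regulatory approval before use, so they are best bundled with another amendment. Beyond that there is at most one short contact per early leaver (0 to 2 in total under the assumption above). Those who refuse contact give no data, and lost on-treatment observation is not restored. If no amendment is made, the SAP change alone still lets late-reported events within 14 days of the last dose count as TEAEs.

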8.2 Definition of an Adverse Event

An AE is any event, side effect, or other untoward medical occurrence that occurs in conjunction with the use of a study drug in humans, whether or not considered to have a causal relationship to this treatment. An AE can, therefore, be any unfavorable and unintended sign (that could include a clinically significant abnormal laboratory finding), symptom, or disease temporally associated with the use of a study drug, whether or not considered related to the study drug. Events meeting the definition of an AE include:

- Exacerbation of a chronic or intermittent pre-existing condition including either an increase in frequency and/or intensity of the condition
- New conditions detected or diagnosed after study drug administration even though it may have been present prior to the start of the study
- Signs, symptoms, or the clinical sequelae of a suspected interaction
- Signs, symptoms, or the clinical sequelae of a suspected overdose of either study drug or a concomitant medication (overdose per se will not be reported as an AE/ serious adverse event [SAE]).

Events that do not meet the definition of an AE include:

- Medical or surgical procedure (e.g., endoscopy, appendectomy); the condition that leads to the procedure is an AE
- Situations where an untoward medical occurrence did not occur (e.g., social and/or convenience admission to a hospital)
- Anticipated day-to-day fluctuations of pre-existing disease(s) or condition(s) present or detected at the start of the study that do not worsen

If there is evidence of an AE through report or observation, the Investigator or designee will evaluate further and record the following information:

- Time of onset and resolution
- Severity
- Causality/relation to study treatment
- Action taken regarding study drug
- Outcome

8.3 Severity of an Adverse Event

Grading the severity of AEs will use the Common Terminology Criteria for Adverse Events (CTCAE) grading system (Version 5.0), as described below. The clinical significance of the AE is determined by the Investigator. The Investigator is encouraged to consult with the Study Director.

- Grade 1 Mild; asymptomatic or mild symptoms; clinical or diagnostic observations only; intervention not indicated
- Grade 2 Moderate; minimal, local or noninvasive intervention indicated; limiting age-appropriate instrumental ADL*.
- Grade 3 Severe or medically significant but not immediately life-threatening; hospitalization or prolongation of hospitalization indicated; disabling; limiting self-care ADL**
- Grade 4 Life-threatening consequences; urgent intervention indicated
- Grade 5 Death related to AE

A semi-colon indicates 'or' within the description of the grade.

*Instrumental Activities of Daily Living (ADL) refer to preparing meals, shopping for groceries or clothes, using the telephone, managing money, etc.

**Self-care ADL refer to bathing, dressing and undressing, feeding self, using the toilet, taking medications, and not bedridden.

Common Terminology Criteria for Adverse Events (CTCAE) Version 5.0. Published: November 27, 2017
https://ctep.cancer.gov/protocoldevelopment/electronic_applications/docs/ctcae_v5_quick_reference_8.5x11.pdf

8.4 Causal Relationship of an Adverse Event

The Investigator will assess the relationship between study drug and the occurrence of each AE. The Investigator's assessment of the relationship of each AE to study drug will be recorded in the source documents and the eCRF. Alternative causes, such as medical history, concomitant therapy, other risk factors, and the temporal relationship of the event to the study drug should be considered and investigated, if appropriate. The following definitions are general guidelines to help assign grade of attribution.

The relationship or association of the AE to a study drug (PLN-74809 or placebo) should be assessed using clinical judgment and the following considerations:

- No Evidence exists that the adverse event has an etiology other than the study drug. For SAEs, an alternative causality must be provided (eg, pre-existing condition, underlying disease, intercurrent illness, or concomitant medication).
- Yes A temporal relationship exists between the AE onset and administration of the study drug that cannot be readily explained by the participant's clinical state or concomitant therapies. Furthermore, the AE appears with some degree of certainty to be related, based on the known therapeutic and pharmacologic actions or AE profile of the study drug. In case of cessation or reduction of the dose, the AE abates or resolves and reappears upon re-challenge.

The relationship to study procedures (such as venipuncture) should be assessed using the following considerations:

- No Evidence exists that the AE has an etiology other than the study procedure
- (not related):
- Yes The AE occurred as a result of protocol-mandated procedures.
- (related):

